#### **10.13.6. Adverse Events and Serious Adverse Events**

If a participant has COVID-19 during the study, this should be reported as an AE or SAE and appropriate medical intervention provided per standard process. If a participant has positive COVID-19 (SARS-CoV2) test, even if asymptomatic, this should be recorded as an AE (see [Section 8.3](#)).

Study treatment should continue unless the investigator/treating physician is concerned about the safety of the participant, in which case temporary or permanent discontinuation may be required.

It is recommended that the investigator discuss temporary or permanent discontinuation of study intervention with the study medical monitor.

#### **10.13.7. Efficacy Assessments**

There will be no alternative measures for efficacy assessments other than what is in the protocol, [Section 8.1](#). It is preferred that participants utilize home health care for efficacy laboratory evaluations. Use of local laboratories will be allowed only if on site or home health care measures cannot be used. If a study participant is unable to visit the site or have home health utilized for protocol-specified laboratory evaluations, testing may be conducted at a local laboratory if permitted by local regulations.

#### **10.13.8. Independent Oversight Committees**

The External Data Monitoring Committee will be informed when this appendix has been utilized.

#### 10.14. Appendix 14: Abbreviations

The following is a list of abbreviations that may be used in the protocol.

Abbreviation	Term
A/C	albumin/creatinine
ADA	anti-drug antibodies
ADE	adverse device effect
AE	adverse event
AESI	adverse events of special interest
ALT	alanine aminotransferase
ANGPTL3	angiopoietin-like protein 3
ApoA	apolipoprotein A
ApoB	apolipoprotein B
ApoC	apolipoprotein C
aPTT	activated partial thromboplastin time
ASCVD	atherosclerotic cardiovascular disease
ASGPR	asialoglycoprotein receptor
ASO	anti-sense oligonucleotide
AST	aspartate aminotransferase
AUC	area under the concentration-time curve
AV	atrioventricular
β-hCG	beta-human chorionic gonadotropin
bpm	beats per minute
BL	baseline
BUN	blood urea nitrogen
CFR	Code of Federal Regulations
CI	confidence interval
CIOMS	Council for International Organizations of Medical Sciences
CK	creatinine kinase
CKD-Epi	Chronic Kidney Disease-Epidemiology Collaboration
C max	maximum observed concentration
CONSORT	Consolidated Standards of Reporting Trials
COVID-19	corona virus disease 19
CRF	case report form
CRO	contract research organization
CS1	clinical study 1
CS2	clinical study 2
CSR	clinical study report
CT	clinical trial
CV	cardiovascular
DILI	drug-induced liver injury
DMC	data monitoring committee
DU	dispensable unit
E-DMC	external data monitoring committee

Abbreviation	Term
EC	ethics committee
ECG	electrocardiogram
eCRF	electronic case report form
EDP	exposure during pregnancy
eGFR	estimated glomerular filtration rate
EMA	European Medicines Agency
E max	maximal effect
EU	European Union
EudraCT	European Clinical Trials Database
FAS	Full Analysis Set
FFA	free fatty acids
FSH	follicle-stimulating hormone
GalNAc	N-acetylgalactosamine
GCP	Good Clinical Practice
GGT	gamma-glutamyl transferase
HbA1c	glycated hemoglobin
HDL	high-density lipoprotein
HDL-C	high-density lipoprotein cholesterol
HFF	hepatic fat fraction
HIPAA	Health Insurance Portability and Accountability Act
HR	heart rate
HRT	hormone replacement therapy
hsCRP	high-sensitivity C-reactive protein
IB	investigator's brochure
ICD	informed consent document
ICH	International Council for Harmonisation
ID	identification
IDL	intermediate density lipoproteins
IMP	investigational medicinal product
IND	investigational new drug
INR	international normalized ratio
IP manual	investigational product manual
IPAL	Investigational Product Accountability Log
IRB	institutional review board
IRT	interactive response technology
ISO	International Organization for Standardization
IWR	interactive web-based response
K2	dipotassium
LDL	low-density lipoprotein
LDL-C	low-density lipoprotein cholesterol
LFT	liver function test
LLN	lower limit of normal
Lp(a)	lipoprotein(a)

Abbreviation	Term
LS	least squares
MCH	mean corpuscular hemoglobin
MCHC	mean corpuscular hemoglobin concentration
MCV	mean corpuscular volume
MMRM	Mixed Model Repeated Measurements
MOE	methoxyethyl
MRI	magnetic resonance imaging
mRNA	messenger ribonucleic acid
msec	millisecond
n	number
N/A	not applicable
NAFLD	nonalcoholic fatty liver disease
NASH	nonalcoholic steatohepatitis
NIMP	noninvestigational medicinal product
NOAEL	no-observed-adverse-effect level
Non-HDL-C	non-high-density lipoprotein cholesterol
PDFF	proton density fat fraction
PCSK9	proprotein convertase subtilisin/kexin type 9
PD	pharmacodynamic(s)
PI	principal investigator
PK	pharmacokinetic(s)
PT	prothrombin time
PVC	premature ventricular contraction/complex
QTc	corrected QT
QTcF	corrected QT (Fridericia method)
QW	every week
Q2W	every 2 weeks
Q4W	every 4 weeks
RBC	red blood cells
SADE	serious adverse device effect
SAE	serious adverse event
SAP	statistical analysis plan
SARS-CoV2	severe acute respiratory syndrome coronavirus 2
SC	subcutaneous(ly)
SoA	schedule of activities
SOP	standard operating procedure
SRSD	single reference safety document
SUSAR	suspected unexpected serious adverse reaction
TBili	total bilirubin
TE	treatment-emergent
TEADA	treatment-emergent anti-drug antibodies
TEAE	treatment-emergent adverse event
TG	triglyceride(s)

Abbreviation	Term
TIMI	Thrombolysis in Myocardial Infarction
T2DM	type 2 diabetes
T max	time to reach C max
UACR	urine albumin: creatinine ratio
ULN	upper limit of normal
US	United States
USADE	unanticipated serious adverse device effect
VLDL	very low-density lipoproteins
VLDL-C	Very low-density lipoprotein cholesterol
WBC	white blood cell
WOCBP	woman of childbearing potential

## 1. VERSION HISTORY

Version/ Date	Associated Protocol Amendment	Rationale	Specific Changes
2 (26 Jun 2020)	Original protocol (03 Jun 2020)	QC review was conducted by following the DMB02-GSOP-RF21 Statistical Analysis Plan Quality Control Checklist	No changes were made to the SAP. QMS05-GSOP-RF06 Quality Control Review Record was filled by [name] after DMB02-GSOP-RF21 Statistical Analysis Plan Quality Control Checklist was reviewed.
1 (08 Jun 2020)	Original protocol (03 Jun 2020)	N/A	N/A

## 2. INTRODUCTION

Note text directly taken from protocol is *italicized*.

This statistical analysis plan (SAP) provides the detailed methodology for summary and statistical analyses of the data collected in Study C4491011. This document may modify the plans outlined in the protocol; however, any major modifications of the primary endpoint definition or its analysis will also be reflected in a protocol amendment.

## 2.1. Study Objectives, Endpoints, and Estimands

Objectives	Endpoints
Primary:	Primary:

 
To estimate the effects of multiple dose levels and regimens of vupanorsen compared to placebo on non-HDL-C.
 
	
 
Percent change from baseline in non-HDL-C at Week 24.
 

Secondary:	Secondary:

 
To estimate the effects of multiple dose levels and regimens of vupanorsen compared to placebo on lipid parameters including TG, ApoB, and LDL-C.
 
To estimate the effects of multiple dose levels and regimens of vupanorsen compared to placebo on ANGPTL3.
 
	
 
Percent change from baseline in TG, ApoB, and LDL-C at Week 16 and Week 24.
 
Percent change from baseline in non-HDL-C at Week 16.
 
Percent change from baseline in ANGPTL3 at Week 16 and Week 24.
 

Safety:	Safety:

 
To evaluate the safety, tolerability, and immunogenicity of multiple dose levels and regimens of vupanorsen.
 
To evaluate the effect of multiple dose levels and regimens of vupanorsen on HFF.
 
	
 
Incidence of treatment-emergent SAEs and AEs throughout the study.
 
Incidence of AESI.
 
Categorical summaries of clinical laboratory abnormalities.
 
UACR.
 
ADA.
 
Change from baseline in AST, ALT, platelet counts, and eGFR.
 
Change and percent change from baseline in HFF (assessed by MRI-PDFF) at Week 24.
 

Tertiary/Exploratory:	Tertiary/Exploratory:

 
To estimate the effects of multiple dose levels and regimens of vupanorsen compared to placebo on total cholesterol, HDL-C, VLDL-C, Lp(a), FFA, ApoB-48, ApoB-100, ApoC-III, and ApoA-I.
 
To estimate the effects of multiple dose levels and regimens of vupanorsen compared to placebo on hsCRP.
 
To evaluate the PK of vupanorsen.
 
	
 
Percent change from baseline at Week 24 in total cholesterol, HDL-C, VLDL-C, Lp(a), FFA, ApoB-48, ApoB-100, ApoC-III, and ApoA-I.
 
Percent change from baseline in hsCRP at Week 24.
 
Plasma concentrations of vupanorsen at Weeks 12, 16, and 24.
 

### 2.1.1. Primary Estimand(s)

*The primary estimand of this study will follow the hypothetical estimand approach to estimate the effect of treatment under the hypothetical condition that all participants maintained their randomized treatment through Week 24. This estimand is meant to estimate the pharmacological effect of the drug when taken as directed. It includes the following 4 attributes:*

- Population: Patients with dyslipidemia taking a statin who meet the inclusion/exclusion criteria.*
- Variable: The percent change from baseline in non-HDL-C at Week 24.*

- *Intercurrent event: All off-treatment data (ie, occurring at least 1 dosing interval after discontinuation of treatment), or data collected post treatment of severe hypertriglyceridemia (ie, change in statin dose or addition of TG lowering therapy; Section 8.2.7), if collected, will be excluded from analysis.*
- *Population-level summary: Difference of variable means between PF-07285557 and placebo.*

### 2.1.2. Secondary Estimand(s)

The primary estimand of secondary endpoints will follow the hypothetical estimand approach to estimate the effect of treatment under the hypothetical condition that all participants maintained their randomized treatment through Week 16 or 24 (as indicated below in Variable). This estimand is meant to estimate the pharmacological effect of the drug when taken as directed. It includes the following 4 attributes:

- Population: Patients with dyslipidemia taking a statin who meet the inclusion/exclusion criteria.
- Variable:
  - Percent change from baseline in TG, ApoB, LDL-C, non-HDL-C, ANGPTL3 at Week 16;
  - Percent change from baseline in TG, ApoB, LDL-C, ANGPTL3 at Week 24.
- Intercurrent event: All off-treatment data (ie, occurring at least 1 dosing interval after discontinuation of treatment), or data collected post treatment of severe hypertriglyceridemia (ie, change in statin dose or addition of TG lowering therapy; Section 8.2.7 of the protocol), if collected, will be excluded from analysis.
- Population-level summary: Difference of variable means between PF-07285557 and placebo.

### 2.1.3. Additional Estimand(s)

#### Estimands of supplementary analyses

In many settings due to intolerance or inadherence, such as discontinuation of treatment or initiation of an add-on therapy when pre-specified criteria are met, including all data collected in the analysis will violate the assumption of the hypothetical estimand.

Following the estimand theory, as detailed in [1], the following two additional estimands will be used for supplemental analyses of primary and key secondary endpoints (ie, at Week 24). The treatment policy estimand estimates the between-group difference of treatment effect without regard to tolerance or adherence to the randomized treatment (eg, receipt of treatment for severe hypertriglyceridemia). The principal stratum

estimand estimates the between-group difference of treatment effect, restricted to the stratum that subjects who adhere to their randomized vupanorsen groups, but regardless of adherence to the placebo group (ie,  $S_{*+}$  in [2]).

### 2.1.3.1. Treatment Policy

- Population: Patients with dyslipidemia taking a statin who meet the inclusion/exclusion criteria.
- Variable:
  - Percent change from baseline in non-HDL-C, TG, ApoB, LDL-C, ANGPTL3 at Week 24 at Week 24.
- Intercurrent event: All off-treatment data (ie, occurring at least 1 dosing interval after discontinuation of treatment), or data collected post treatment of severe hypertriglyceridemia (ie, change in statin dose or addition of TG lowering therapy; Section 8.2.7 of the protocol), if collected, will be included in the analysis.
- Population-level summary: Difference of variable means between PF-07285557 and placebo.

### 2.1.3.2. Principal Stratum Estimand

- Population: Patients with dyslipidemia taking a statin who meet the inclusion/exclusion criteria.
- Variable:
  - Percent change from baseline in non-HDL-C at Week 24;
  - Percent change from baseline in TG, ApoB, LDL-C, ANGPTL3 at Week 24.
- Intercurrent event: Subjects with off-treatment data (ie, occurring at least 1 dosing interval after discontinuation of treatment), or with data collected post treatment of severe hypertriglyceridemia (ie, change in statin dose or addition of TG lowering therapy; Section 8.2.7) in the vupanorsen groups, will be excluded from analysis. However, data of such subjects in the placebo group, will be included in the analysis.
- Population-level summary: Difference of variable means between vupanorsen and placebo.

### Estimands of sensitivity analyses

Hypothetical estimand.

## 2.2. Study Design

*This is a multicenter, randomized, double-blind, placebo-controlled, dose-ranging, 8-arm parallel-group study in adults  $\geq 40$  years of age with dyslipidemia who are on a stable dose of a statin (with or without ezetimibe). Following the Screening Period to confirm eligibility, a total of approximately 260 participants will be randomized in the study to receive SC doses of vupanorsen or placebo administered Q2W or Q4W for the purpose of assessing efficacy, safety, and tolerability of vupanorsen. The total duration of treatment in the study is 24 weeks with an additional 12-week safety follow-up period.*

*The sponsor, along with academic leadership of the study (TIMI Study Group), will monitor the proportion of participants enrolled according to statin intensity to ensure that an adequate number of participants on high intensity statin are enrolled. High intensity statin use is defined as atorvastatin (40 mg or 80 mg per day) or rosuvastatin (20 mg or 40 mg per day). All other statin regimens are considered low or moderate intensity. Approximately 40% or more of participants enrolled should be on high intensity statin therapy, and enrollment of participants using low/moderate intensity statin may be capped.*

*Vupanorsen dosing will be accomplished by administration of 1 or 2 prefilled syringes of either 60 mg or 80 mg strength according to required total dose. Placebo will be provided as a prefilled syringe and will be administered as either 1 or 2 syringes. See Table 1 for the dosing plan.*

**Table 1. Dosing Plan**

Treatment Arm	Total Monthly Dose	Injection Regimen	Number of Participants
Placebo	0 mg	Single or double injection Q2W or Q4W	40
80 mg Q4W	80 mg	Single injection Q4W	20
60 mg Q2W	120 mg	Single injection Q2W	20
120 mg Q4W	120 mg	Double injection Q4W	20
80 mg Q2W	160 mg	Single injection Q2W	40
160 mg Q4W	160 mg	Double injection Q4W	40
120 mg Q2W	240 mg	Double injection Q2W	40
160 mg Q2W	320 mg	Double injection Q2W	40

## 3. ENDPOINTS AND BASELINE VARIABLES: DEFINITIONS AND CONVENTIONS

### 3.1. Primary Endpoint(s)

- *Percent change from baseline in non-HDL-C at Week 24.*

### 3.2. Secondary Endpoint(s)

- *Percent change from baseline in TG, ApoB, and LDL-C at Week 16 and Week 24;*

- *Percent change from baseline in non-HDL-C at Week 16;*
- *Percent change from baseline in ANGPTL3 at Week 16 and Week 24.*

### 3.3. Other Endpoint(s)

The following safety endpoints and tertiary/exploratory endpoints will also be analyzed and reported.

#### Safety endpoints:

- Change from baseline in AST, ALT, platelet counts, and eGFR;
- Change and percent change from baseline in liver fat (assessed by MRI-PDFF) at Week 24;
- Percent change from baseline in UACR.

#### Tertiary/Exploratory:

- Percent change from baseline at Week 24 in total cholesterol, HDL-C, VLDL-C, Lp(a), FFA, ApoB-48, ApoB-100, ApoC-III, and ApoA-I;
- Percent change from baseline in hsCRP at Week 24.

### 3.4. Baseline Variables

*If the baseline value is not available, the last measurement during screening prior to the randomization visit will be used. However, for non-HDL-C and other lipid parameters, the baseline value will be calculated using the average of all values obtained at Screening and on Day 1 prior to dosing, except that for TG, when the initial value is exclusionary, the repeat value after the initial value and Day 1 value will be used to derive the baseline value.*

### 3.5. Safety Endpoints

- *Incidence of treatment-emergent SAEs and AEs throughout the study;*
- *Incidence of AESI;*
- *Categorical summaries of clinical laboratory abnormalities;*
- *UACR;*
- *ADA;*
- *Change from baseline in AST, ALT, platelet counts, and eGFR;*
- *Change and percent change from baseline in liver fat (assessed by MRI-PDFF) at Week 24.*

### 3.5.1. Adverse Events

Treatment-emergent AE is defined as any adverse event with an onset date no earlier than the first dose of study medication.

A 3-tier approach will be used to summarize AEs. Different analyses will be performed for different tiers (see [Section 6.6.1](#)).

Tier 1 events: These are prespecified events of clinical importance and are maintained in a list in the product's Safety Review Plan.

The full list is not restricted to the following. As the study is ongoing, the study team will monitor all adverse events on a blinded basis and hence the list might be updated accordingly in the safety review plan.

- Injection site reactions.

Tier 2 events: These are events that are not tier 1 but are “common.” A Medical Dictionary for Regulatory Activities (MedDRA) preferred term (PT) is defined as a Tier 2 event if there are at least 10% in one or more treatment groups.

Tier 3 events: These are events that are neither Tier 1 nor Tier 2 events. For this study, tier 3 events won't be reported separately, but will be included in the overall AE summary tables.

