### **6. STUDY INTERVENTION**

Study intervention is defined as any investigational intervention(s), marketed product(s), placebo, medical device(s), or study procedure(s) intended to be administered to a study participant according to the study protocol.

For the purposes of this protocol, study intervention refers to vupanorsen or placebo administered SC.

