### **6.1.1. Administration**

During the Screening Period, sites will instruct participants (or caregivers) how to perform the SC injection and proper sterile technique. Participants (or caregivers) will be dispensed a prefilled syringe of open-label placebo to inject, and sites will determine if a participant or caregiver is willing and able to correctly perform the SC injection.

On Day 1, the initial dose of study intervention administered by the participant or caregiver must be observed by study site personnel to ensure the participant or caregiver is using proper technique.

Vupanorsen or placebo will be administered as a single or double SC injection at 2-week or 4-week intervals depending on the treatment arm. At the study site or at home, SC injections should be administered by the participant or caregiver according to dosing instructions in any of the following locations: upper arm, thigh, or abdomen quadrant, as preferred by the participant. Participants receiving 2 injections should consecutively administer each injection in a different location. To minimize injection site reactions, the SC injection should not be administered in areas where the skin is burned, reddened, inflamed, swollen, or scarred. If a participant receiving study intervention Q2W or Q4W misses or delays their dose outside the dosing window and is within 7 or 14 days, respectively, of the next dose, the dose should be skipped altogether and recorded on the CRF.

Participants receiving study intervention Q2W will receive a diary to record home dosing. Study intervention administration details will be recorded on the CRF.

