### **8.3.1. Time Period and Frequency for Collecting AE and SAE Information**

The time period for actively eliciting and collecting AEs and SAEs (“active collection period”) for each participant begins from the time the participant provides informed consent, which is obtained before the participant’s participation in the study (ie, before undergoing any study-related procedure and/or receiving study intervention), through and including a minimum of 12 weeks, except as indicated below, after the last administration of the study intervention.

Follow-up by the investigator continues throughout and after the active collection period and until the AE or SAE or its sequelae resolve or stabilize at a level acceptable to the investigator and Pfizer concurs with that assessment.

For participants who are screen failures, the active collection period ends when screen failure status is determined.

If the participant withdraws from the study and also withdraws consent for the collection of future information, the active collection period ends when consent is withdrawn.

If a participant definitively discontinues or temporarily discontinues study intervention because of an AE or SAE, the AE or SAE must be recorded on the CRF and the SAE reported using the CT SAE Report Form.

Investigators are not obligated to actively seek AEs or SAEs after the participant has concluded study participation. However, if the investigator learns of any SAE, including a death, at any time after a participant has completed the study, and he/she considers the event to be reasonably related to the study intervention, the investigator must promptly report the SAE to Pfizer using the CT SAE Report Form.

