#### **9.4.5. Other Safety Analyse(s)**

All safety analyses will be performed on the safety population.

From the safety perspective, the following key laboratory endpoints will be explored:

- Change and percent change from baseline in HFF at Week 24
- Change from baseline in eGFR
- Change from baseline in ALT/AST
- Percent change from baseline in UACR
- Percent change from baseline in platelet counts
- Summary of ALT/AST abnormalities
- Summary of confirmed thrombocytopenia

TEAEs, SAEs, death, injection site reactions, ADA, ECGs, vital signs, immunogenicity, and other safety laboratory data, including categorical abnormalities in laboratory data, will be summarized/analyzed, listed, or presented in figures by treatment group or by treatment group and by visit where appropriate. All safety data, including data collected post the occurrence of intercurrent events, will be reported.

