

• Any abnormal laboratory test results (hematology, clinical chemistry, or urinalysis) or other safety assessments (eg, ECG, radiological scans, vital sign measurements), including those that worsen from baseline, considered clinically significant in the medical and scientific judgment of the investigator. Any abnormal laboratory test results that meet any of the conditions below must be recorded as an AE:

• Is associated with accompanying symptoms.

• Requires additional diagnostic testing or medical/surgical intervention.

• Leads to a change in study dosing (outside of any protocol-specified dose adjustments) or discontinuation from the study, significant additional concomitant drug treatment, or other therapy.

• Exacerbation of a chronic or intermittent preexisting condition including either an increase in frequency and/or intensity of the condition.

• New conditions detected or diagnosed after study intervention administration even though it may have been present before the start of the study.

• Signs, symptoms, or the clinical sequelae of a suspected drug-drug interaction.

• Signs, symptoms, or the clinical sequelae of a suspected overdose of either study intervention or a concomitant medication. Overdose per se will not be reported as an AE/SAE unless it is an intentional overdose taken with possible suicidal/self-harming intent. Such overdoses should be reported regardless of sequelae.

• The signs, symptoms, and/or clinical sequelae resulting from lack of efficacy will be reported as an AE or SAE if they fulfill the definition of an AE or SAE and meet the requirements as per Section 8.3.8.1. Also, “lack of efficacy” or “failure of expected pharmacological action” does not constitute an AE or SAE.

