#### **Follow-up of AEs and SAEs**

- The investigator is obligated to perform or arrange for the conduct of supplemental measurements and/or evaluations as medically indicated or as requested by the sponsor to elucidate the nature and/or causality of the AE or SAE as fully as possible. This may include additional laboratory tests or investigations, histopathological examinations, or consultation with other healthcare providers.
- If a participant dies during participation in the study or during a recognized follow-up period, the investigator will provide Pfizer Safety with a copy of any postmortem findings including histopathology.
- New or updated information will be recorded in the originally completed CRF.
- The investigator will submit any updated SAE data to the sponsor within 24 hours of receipt of the information.

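### The SAP defines a treatment-emergent AE by onset date alone, so a Screening AE that worsens or becomes serious after the Day 1 dose may be left out of the safety endpoint, depending on how the site records it

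*SAP*

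**What the plan says.** SAP 3.5.1 states: "Treatment-emergent AE is defined as any adverse event with an onset date no earlier than the first dose of study medication". The definition serves a listed safety endpoint in SAP 3.5, "Incidence of treatment-emergent SAEs and AEs throughout the study". The same SAP section goes on to the three-tier AE scheme. A preferred term becomes Tier 2 when it reaches 10% in at least one treatment group, and SAP 6.6.1 then gives it a risk difference against placebo with a 95% confidence interval.

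Three parts of the protocol bear on which onset date an event carries:

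- Section 8.3.1: the active collection period "begins from the time the participant provides informed consent". By the Schedule of Activities, Screening lasts up to 28 days and AE monitoring takes place at all three Screening visits.
- Appendix 3 (10.3.3), on follow-up: "New or updated information will be recorded in the originally completed CRF".
- Appendix 3 (10.3.1), among the events that count as AEs: "Exacerbation of a chronic or intermittent preexisting condition including either an increase in frequency and/or intensity of the condition".

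Section 9.4.5 names SAEs and deaths alongside TEAEs and adds: "All safety data, including data collected post the occurrence of intercurrent events, will be reported".

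**The concern.** A treatment-emergent count is meant to capture what happens to participants once they are on study treatment, and that includes deterioration of something already present. An onset-only rule captures new events and leaves deterioration to the way the CRF entry happens to be kept. If a site updates the existing entry, the event keeps its pre-dose onset and fails the test, even if it has become severe or serious on treatment. If the site opens a new entry, the same clinical course passes.

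At stake are the completeness of a stated safety endpoint and its consistency across sites. In arms this small, the rule could also affect whether a preferred term qualifies for a Tier 2 risk difference.

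**Working it through.** The plan states no figure that depends on this definition, so there is nothing to reproduce. The check is a reading of the two documents side by side, followed by a scale calculation.

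**Step 1. Is there a worsening clause elsewhere?** I found none in SAP 3.5, 6.3.1 or 6.6.1, nor in Protocol 9.4.5. SAP 3.5.1 is the only definition.

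**Step 2. Can a pre-dose AE be in the database?** Yes. Collection starts at consent and the Schedule of Activities has AE monitoring throughout Screening.

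**Step 3. What happens when such an AE worsens or becomes serious after Day 1?** The protocol supports two ways of recording it:

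| Recording route | Basis | Onset date held | Meets SAP 3.5.1? |
|---|---|---|---|
| Existing entry updated | Appendix 3, follow-up rule (10.3.3) | In Screening | No |
| New entry for the exacerbation | Appendix 3, AE definition (10.3.1) | After Day 1 | Yes |

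Neither document chooses between the routes. The second is least secure in two cases. One is an acute event that first arose in Screening, which is not obviously a chronic or intermittent preexisting condition. The other is an event whose only change is that it becomes serious, because the exacerbation wording speaks of frequency and intensity.

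**Step 4. Scale of one participant.** Inputs: arm sizes of 20 and 40 (dosing plan, SAP Table 1) and the 10% Tier 2 threshold (SAP 3.5.1).

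- Share of an arm = 1/N: 1/20 = 5.0 percentage points; 1/40 = 2.5 percentage points.
- Tier 2 threshold = 0.10 × N: 0.10 × 20 = 2 participants; 0.10 × 40 = 4 participants.

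In a 20-participant arm, one omitted participant can be the difference between 1 and 2, that is, between a term with no separate estimate and a term with a risk difference and interval. For overall AE incidence the 5.0 and 2.5 points are upper bounds, because a participant who has any other TEAE is already counted.

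These figures show what one event is worth. They are not an expected bias, because the documents give no rate of Screening events that worsen after dosing.

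**The case against.** The strongest reply is that little is lost. It has four parts:

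- Exacerbation is an AE in its own right under Appendix 3, so a site may well enter it with a post-dose onset, and it would then be counted.
- The follow-up rule is general. It does not mention onset dates or severity changes, and any CRF completion guidelines are not among the documents.
- The protocol's named risks are largely covered by other means. Laboratory worsening appears in change-from-baseline, shift and categorical summaries (SAP 6.3.1 and 6.6.2). Injection site reactions, the only Tier 1 event the SAP names, begin after an injection.
- SAP 6.6.1 describes the safety analysis as generally exploratory.

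Most of this stands, and it limits the point. A reader might infer that worsening Screening events are never counted, or are lost from the report. The documents do not support that: the exacerbation route exists, and Protocol 9.4.5 commits to reporting all safety data. A reader might also infer that the rule can only hide drug-related harm. That does not follow either, because the rule applies equally to placebo, and an omission there moves a risk difference the other way.

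What the reply does not remove is the gap itself. A clinical AE that worsens has no counterpart to the laboratory shift tables, and the SAE summary listed in SAP 6.3.1 is the treatment-emergent one. An endpoint should not depend on a recording choice that neither document settles.

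A further tempting reading concerns the open-label placebo injection used for training in Screening. Section 6 says "study intervention refers to vupanorsen or placebo administered SC", so one might argue that this injection starts the treatment-emergent period. The protocol rules this out: Section 6.1.1 places the initial dose of study intervention on Day 1, and the Schedule of Activities counts days from the start of study intervention on Day 1.

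**Conclusion.** The point holds as a gap in a definition that should be closed. SAP 3.5.1 is onset-only, and the documents leave open whether a Screening-onset AE that increases in severity or becomes serious after the Day 1 dose receives a new onset date. Such an event may be missing from the treatment-emergent incidence endpoint and from Tier 2 selection and risk differences, while still appearing in overall safety reporting.

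The size cannot be estimated from the documents. It is bounded only per participant, at the 5 and 2.5 points shown above. No sample size, power or efficacy figure is affected.

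The conclusion rests on two assumptions: that no CRF guideline outside these documents already settles the matter, and that the tier tables are built on treatment-emergent events. SAP 3.5.1 implies the second by placing the definition at the head of the tier scheme, but does not say it outright.

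**What to change.** In SAP 3.5.1, define a TEAE as an AE that starts on or after the first randomized dose on Day 1, or that started earlier and increased in severity or became serious on or after that dose.

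Add a matching CRF completion instruction so that the date of worsening is captured. The simplest form is a new AE entry dated at the worsening when a pre-dose AE increases in severity or becomes serious after Day 1. Without that date the revised definition cannot be programmed reliably.

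The cost is one sentence in the SAP, one site instruction and a small programming change. It should be done before unblinding. No additional assessments are needed.
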